Intranasal Oxytocin:
A Neuropharmacological Intervention for Maternal Neglect?

H-26732

December 31, 2024

Study Protocol

The purpose of this study is to explore how oxytocin may modify early maternal brain and behavioral responses to infant cues. This study will examine a potential pharmacological intervention for maternal neglect which targets core neurobiological deficits. This may eventually be used to supplement and augment other psychosocial and behavioral interventions.

Initial enrollment: Recruitment occurred during the postpartum period using EPIC medical records and advertising via newspaper, internet, public postings, etc. Once eligibility was confirmed, subjects were scheduled for a study visit where they provided informed consent before participating in any study activities.

Visit 1: 4 Months Postpartum – Adult Attachment Interview (AAI). During this visit, each enrolled woman participated in a modified version of the Adult Attachment Interview (AAI), a semi-structured 1½-2 hour-long interview involving specified questions and follow-up inquiries relating to childhood relationships with attachment figures. The modified version was chosen because of its theoretical links with patterns of information processing in the brain. Each digitally recorded interview was transcribed (with personally identifying details altered to preserve anonymity), and coded blindly to classify each woman's adult attachment pattern. We also collected sociodemographic and breastfeeding data, and screened for postpartum depression using the Edinburgh Postnatal Depression Scale (EPDS).

Visits 2A&B and 3A&B: Intranasal Oxytocin vs. Placebo Administration. In this double-blinded cross-over placebo-controlled trial of intranasal oxytocin, maternal brain and behavioral responses to infant cues were assessed within and between subjects. Each participant was administered both the active (oxytocin) and inactive (placebo) nasal spray just prior to separate behavioral or fMRI scanning sessions, with the order of administration balanced across subjects. All involved were blinded to the identity of the oxytocin or placebo sprays. Before each visit, the mother was asked to abstain from tobacco, food and drink (except water) for at least 2 hours prior to the visit. We attempted to schedule visits during the latter half of the mother's menstrual cycle, to minimize potential confounding from fluctuations in estrogen levels. Mothers without regular menstrual cycles were attempted to be scheduled one month apart. Mothers who were still breastfeeding were asked to feed their infant at least one hour prior to the visit.

For the four visits involving intranasal drug administration (two behavioral testing visits and two fMRI scanning visits), the following protocol applied: participants were given a urinary pregnancy test prior to the start of each visit. If a mother tested positive, she was excluded from the study due to theoretical concern about possible effects of oxytocin on uterine contraction. Just prior to drug administration, the mother completed the Positive and Negative Affect Scale (PANAS) to rate her current emotions, for comparison to post-spray. The mother then self-administered a dose of either oxytocin (3 puffs per nostril [4 IU per puff] = 24 IU total) or a placebo spray containing only the inactive ingredients of the oxytocin solution. Both experimenters and subjects were blind to the treatment they are receiving. A stopwatch was started at the moment the subjects began the intranasal administration, so that the behavior assessment or fMRI scanning could begin approximately 50 minutes later. Forty minutes after drug administration, the PANAS was repeated.

Visits 2A&B: 5-6 Months Postpartum – Behavioral Response. On arrival, the mother and infant were escorted into a behavioral observation room at the Clinical Nutrition Research Center, where the infant was introduced to some developmentally appropriate toys. Questionnaires completed at home were reviewed (Infant Behavior Questionnaire [IBQ], Parenting Stress Index [PSI] and demographics and breastfeeding questionnaire), and if incomplete, were completed at this time. Each mother then self-administered the nasal spray, which had been previously randomized by the investigational pharmacy to be either oxytocin or placebo. During the waiting period, the Bayley Scales of Infant Development screener was completed with the infant, to exclude developmental delays in areas of fine motor, gross motor, language or social development. This was performed by a research associate who has been trained in the use of this standardized tool. Fifty minutes after the nasal spray was administered, each mother rejoined her infant to participate in a videotaped "free play" interaction on the floor for 3 minutes. The recording was later coded for dyadic interactions using a

14-point sensitivity scale in the CARE-Index. A modified still-face procedure was then conducted. The mother was then taken to another area of the building, while the infant was videotaped to obtain face images used during the subsequent scanning visits. During the brief separation period, the infant was secured in a mounted car seat, and videotaped while using age appropriate toys to elicit smiling (and neutral) facial expressions. This did not usually last no more than 10 minutes. The mother did not observe the videotaping to ensure that each infant face image was novel when presented during the subsequent visits. Crying faces were also elicited by briefly leaving the infant alone in the room, if necessary, secured in the car seat, while the video recorder was running. The infant was observed at all times from behind a one-way mirror, and only left to cry for around 35-40 seconds. Infant cry was also recorded at that time. Infant face images with various degrees of affect—happy, neutral and sad—were then extracted from the digital video recording, for use in the subsequent fMRI procedure (Visit 3). The images were standardized for size, orientation and background using Adobe Photoshop. All of the face images were rated on degree of affect using a 5-point adaptation of the Self-Assessment Manikin (SAM), categorizing each image into one of five affect groups: very happy, happy, neutral, sad or very sad. These faces were matched on age, sex, ethnicity and degree of affect with a large database of “unknown” infant faces, collected during a previous study. Approximately one month later the basic procedure was repeated for each subject, except that those who received intranasal oxytocin were given placebo, and vice versa.

Visit 3A&B: 8-9 Months Postpartum – Brain Response. Around three months after the first behavioral response session, each mother attended two scanning sessions at the Human Neuroimaging Laboratory, Baylor College of Medicine. Intranasal oxytocin or placebo was again administered as described above. Infant face images from Visit 2A were used in the Visit 3A scanning session, and Visit 2B with 3B, to ensure that the repeat scanning session used comparable but unique face images. The images from both sessions were matched on degree of facial affect.

Prior to intranasal drug administration on the first scanning visit, the mother completed the Positive and Negative Affect States (PANAS) questionnaire. During the waiting period, the mother completed questionnaires. Fifty minutes after the administration of the nasal spray, the mother participated in the functional MRI scanning session, passively viewing a series of unique infant face images and hearing cries of her own infant and of an unknown infant. Each parent was informed that their “brain activity will be monitored using functional MRI while you are shown pictures of your own baby”. Using an event-related fMRI design, randomly presented images were viewed for 2 seconds, with a random inter-stimulus interval of 2, 4 or 6 seconds. The 60 images were equally divided into 3 affect groups – happy, neutral or sad, with the intensity of happy and sad affect balanced between the “own” and “unknown” faces. The order of the images from each of the 6 groups (own-happy [OH], own-sad [OS], unknown-happy [UH], unknown-sad [US]) were pseudo-randomized within the run, but not between subjects. All imaging was performed using a 3 Tesla Siemens MRI scanner. Visual images were generated using a computer controlled LCD projector, and presented to the mother via an overhead mirror display. Regional brain activation was assessed by measuring changes in blood-oxygen-level-dependent functional MRI signal (BOLD-fMRI). Subjects participated in a single whole-brain functional run of around 185 scans each. High-resolution T1-weighted structural images were acquired. After the scanning session, each mother was asked to rate each of the infant face images on how they thought the infant was feeling, as well as their own feelings of pleasure or arousal, using an adaptation of the Self-Assessment Manikin.

Statistical Analysis Plan

fMRI Data Processing and Analysis:

Imaging data for each subject was preprocessed and analyzed using the following steps:

Head motion correction was performed by spatial alignment of all brain volumes to the first volume by rigid body transformations. Slice scan time correction was performed using sinc interpolation, based on the repetition time (TR) and order of slice scanning (ascending interleaved). Following linear trend removal, low frequency nonlinear drifts of 3 or less cycles was removed using a temporal high pass filter. Spatial smoothing will not be performed. The anatomical dataset underwent iso-voxel scaling to 1 x 1 x 1 mm resolution and was transformed into sagittal orientation. It was then transformed into AC/PC and MNI standard space. Functional runs for each subject were then coregistered with the anatomical 3-dimensional dataset, iso-voxel transformed, and then transformed into standard ACPC and MNI coordinate space, resulting in normalized 4-dimensional volume-time course data.

For each functional run of the event-related data, a protocol file was created, representing the timing of each stimulus event. The four infant face stimulus types in the design matrix included Own-Happy (OH), Own-Sad (OS), Unknown-Happy (UH), and Unknown-Sad (US). Each predictor was convolved with a double-gamma hemodynamic response function (Friston, Fletcher, Josephs et al. 1998). Using the General Linear Model (GLM), group effects were evaluated using a random effects analysis, with a percent time course transformation applied to each subject separately. In the random effects analysis, statistical maps were created for each individual subject before being subjected to a second level of statistical analysis, allowing generalization to the sample population of first-time mothers. Main effects and possible interaction effects of infant "identity" and "affect" were explored using 2-factor repeated measure ANOVAs. Group t-maps (2-tailed) were also generated after specifying a particular contrast in stimulus types (e.g. OH>UH), and were visualized on an averaged 3D anatomical image, which was created from all of the individual subject images. Corrections were made for multiple comparisons.

Next, activation patterns were compared between oxytocin treatment groups and attachment groups using a mixed-model repeated measures analysis of variance (ANOVA), with fixed effects analyses for 1) "infant face category" as a repeated measure within-subjects variable, 2) "oxytocin treatment group" as a within- and between-subjects variable, and 3) "attachment group" as a between-subjects variable. Subjects were treated as a random effect within each group and were used to test for face affect x treatment group x attachment group interaction effects on brain function. Mean beta weights were calculated and compared between the two treatment and attachment groups, in *a priori* regions of interest (VTA, ventral striatum, medial prefrontal cortex), using the t-test and the Mann-Whitney U-test for non-parametric data.

Brain/Behavior Analyses:

The relationship between brain response to the visual infant stimuli described above and interview derived measures was examined within the general linear model framework. Measures examined in this manner included ratings of the stimuli obtained immediately after scanning, adult attachment classifications, and ratings of the parent-infant interaction session ("maternal sensitivity" score). Initially, percent signal change data was extracted from regions of interest, including mesocorticolimbic pathway (VTA, ventral striatum, medial prefrontal cortex), nigrostriatal pathways (substantia nigra, dorsal striatum, dorsolateral PFC), as well as the amygdala, hippocampus, anterior insula and hypothalamus, and was entered into regression models to determine whether there was a linear relationship between brain activation in response to the stimuli and behavioral scores. We focused on these regions given data from animal and human studies reviewed that implicate them in attachment and/or fear neurocircuitry (Leibenluft, Goblin, Harrison et al. 2004a; Lorberbaum, Newman, Horwitz et al. 2002a; Nitschke, Nelson, Rusch et al. 2004; Seifritz, Esposito, Neuhoff et al. 2003; Strathearn et al., 2008; Swanson, 2000). Regression models also tested for group differences in the relationship between brain activation and behavior. Regions of interest were defined using high resolution 3D

images normalized to standardized stereotactic space (Collins, Zijdenbos, Kollokian et al. 1998). Measures of the striatum included caudate and putamen, outlined on each slice in which these structures were visible. Regression analyses were further employed to identify areas that show a continuous linear dose-response function.

Analyses by Hypotheses:

Since the study is a crossover design, the model initially contains terms testing the order of treatment (oxytocin/placebo) and the interaction between order and treatment to ensure detection of any unexpected carry-over effect from treatment. Since a sufficient washout period was provided and different pictures were shown on the two occasions, we expected these terms to be non-significant, in which case they were removed from the model.

Hypotheses 1-3 was tested using a generalized estimating equation model (SPSS version 17.0), which accounts for repeated measures in the crossover design as well as different types of dependent variables. The basic model contains terms for testing each of these hypotheses including treatment, attachment and treatment x attachment. Interpretation began with the treatment x attachment interaction. If this interaction was not significant, it was omitted from the model. Attachment was initially be treated as a 4-category variable (Types A, B, C and A/C), with the main comparisons being between Types A and B, and between Types C and B. However, we also combined categories to examine secure (Type B) vs. insecure (Types A, C, A/C) attachment. In addition, for the brain-related outcomes, we looked at infant affect as an additional within-subject factor, and examined possible 3-way interactions – treatment x attachment x affect. If this interaction was significant the data was split on attachment group and reanalyzed to assess the treatment x affect interaction within attachment groups. If this interaction was not significant, it was removed. A positive finding for this interaction would indicate splitting on attachment group and reanalysis is in order to assess treatment effect within these groups. Main effects of treatment, attachment, and affect remained in the model. Hypothesis 2(ii) involving counts showed a Poisson distribution outcome while the others showed a normal distribution.

We will also included in the model stratification variables such as maternal age, ethnicity, breastfeeding status and income. Finally, we explored differences between attachment groups on measures of psychopathology, such as depression (from BDI), anxiety (from SSTA) and parenting experience (from the PSI). If differences emerged between attachment groups in these measures, we considered including them as covariates in analyses.

Hypothesis 4 assessed the correlation between maternal brain reward activation (ventral striatum and medial prefrontal cortex) and three indirect measures of maternal neglect using a linear model.

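### Each scan shows only one filming session's infant images: this adds avoidable noise to the fMRI contrast and, if the Visit 3 spray order was tied to the Visit 2 order, confounds scan treatment with the spray given at filming

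*Combined protocol and SAP*

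**What the plan says.** The Study Protocol describes two crossovers in the same mothers: two behavioural visits (2A, 2B) and two scanning visits (3A, 3B). Spray order is described once for all of them: "with the order of administration balanced across subjects".

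At each behavioural visit the mother takes the spray, has a short free play with her infant about 50 minutes later, and then does a modified still-face. Filming follows: "The mother was then taken to another area of the building, while the infant was videotaped to obtain face images used during the subsequent scanning". For the second behavioural visit, "Approximately one month later the basic procedure was repeated for each subject, except that those who received intranasal oxytocin were given placebo, and vice versa".

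The section on Visit 3A&B assigns the images: "Infant face images from Visit 2A were used in the Visit 3A scanning session, and Visit 2B with 3B". The stated purpose is "to ensure that the repeat scanning session used comparable but unique face images". It adds: "The images from both sessions were matched on degree of facial affect". The spray at Visit 3 is said only to be given again as before. No rule links its order to the Visit 2 order or makes the two independent.

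The SAP, under Analyses by Hypotheses, first fits order and order-by-treatment terms and removes them if non-significant. One reason given for expecting that is that "different pictures were shown on the two occasions". No term is planned for the spray the mother had received when the images were filmed.

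**The concern.** The fMRI question is how oxytocin changes a mother's brain response to infant cues. Within any one mother, the oxytocin and placebo scans differ in spray and also in image set: another filming session, an infant about a month older or younger, and images recorded after the opposite spray. Matching on affect equalises the rated affect level, not everything else about the images.

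Two things are at stake. The first is precision: a mother's response to one set rather than the other goes into her treatment difference. The second is identifiability: if the two spray schedules are linked, the stimulus difference follows the drug rather than the visit, and the planned order terms cannot detect or remove it. The SAP treats the different pictures as reassurance about carry-over and does not consider them as a second difference between the scans.

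**Working it through.** The plan gives no figure to reproduce: no sample size, SD or effect size is stated. The check is on the structure of the design.

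**Inputs from the documents**
- Set 2A is shown only at 3A, and set 2B only at 3B (Visit 3A&B).
- The two sets were filmed after opposite sprays (Visits 2A&B).
- Order is balanced across mothers (Visits 2A&B and 3A&B).

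**Assumed, because not stated**
- q: share of mothers with oxytocin at the first scan; 0.5 under balance.
- p: share of mothers whose Visit 3 order repeats their Visit 2 order; range 0 to 1.
- δ: average response to set 2B minus set 2A, which is also the period effect; unknown.
- d: average response to images filmed after oxytocin minus images filmed after placebo, at equal rated affect; unknown.
- t²: mother-specific image-set variance per scan. s²: all other within-mother variance per scan. Range used for t²/s²: 0.10 to 0.25.

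**Step 1. Image set as a period effect.** A mother scanned on oxytocin first has an expected oxytocin-placebo difference of τ − δ; one scanned on placebo first has τ + δ. The mean is τ + (1 − 2q)δ.
- q = 0.50: bias 0. The correlation of image set with scan treatment is 0.00, however the two orders are related.
- q = 0.45: bias 0.10δ. q = 0.40: bias 0.20δ.

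Reading order as treatment sequence, the SAP's order-by-treatment term in a 2×2 crossover is this period effect. Dropping it under exact balance adds no bias, but multiplies the variance of the differences by 1 + (δ/SD)², where SD is that of the differences within a sequence: 1.04, 1.25 and 1.64 for δ/SD = 0.2, 0.5 and 0.8.

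**Step 2. Spray at filming.** A mother with the same order at both crossovers has expected difference τ + d; one with opposite orders has τ − d. The mean is τ + (2p − 1)d.

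| p | Bias |
|---|---|
| 1 | +d |
| 0.75 | +0.5d |
| 0.5 | 0 |
| 0.25 | −0.5d |
| 0 | −d |

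The model with intercept, sequence, period, scan treatment and spray at filming has rank 5 of 5 when the orders are independent. When they are always the same or always reversed, the rank is 4 of 5 and the correlation of filming spray with scan treatment is +1.00 or −1.00. Balance of order does not help then, because d follows the drug and not the visit.

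**Step 3. Noise, whatever the order rule.** With session-specific sets, the variance of a mother's difference is 2(s² + t²). If each scan draws half its own-infant images from each session, the session effects are equal in both scans and cancel, leaving 2s². The share removed is t²/(s² + t²).
- t²/s² = 0.10: 0.10/1.10 = 9%.
- t²/s² = 0.25: 0.25/1.25 = 20%.

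A period term removes only the average shift δ, not this mother-specific part.

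**Step 4. Feasibility.** Visit 2B is about one month after 2A, and 3A about three months after 2A. Both sets therefore exist roughly 3 − 1 = 2 months before the first scan. If the 60 images per scan are spread evenly over six groups, each group has 60/6 = 10. Each session now supplies 10 own-infant images per affect level to one scan; under a split it would supply 5 to each of two scans, still 10.

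**The case against.** The case on the other side is substantial.

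- **Balance.** About half the mothers see set 2A under oxytocin and half under placebo, so a set effect, including infant age and filming session, cancels from the average contrast. This stands, for as long as order is balanced among the mothers analysed. The documents state balance across subjects; they do not state it within the attachment groups on which the data may be split.
- **Weak path for d.** The infant received no spray, the mother was elsewhere during filming, and expressions were elicited with toys or by a brief period alone. The mother's spray could act only through the preceding free play and still-face. This stands as a reason to think d may be small, though not as evidence that it is zero.
- **Existing safeguards.** The two sets were matched on affect and the images standardised. The unknown faces were matched on infant age, sex and ethnicity as well as affect, which limits an age effect in own-versus-unknown contrasts. This stands in part. The unknown faces come from an earlier study and carry no effect of this mother's spray, so they cannot cancel d.
- **Chance mismatch.** If the two orders were assigned independently, p will differ from 0.5 by chance. That is random error with expectation zero, not bias, and should not be counted as such.
- **Assumed ratios.** The 9-20% rests on an assumed variance ratio. This stands: it shows a plausible scale and is not an estimate for this trial. The added noise widens intervals but does not invalidate them.
- **Timing.** The text reads as a completed study, so images can probably no longer be reassigned. The analysis remedies still apply.

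**Conclusion.** The point holds in a limited, conditional form. Image set is identical to scan period, and the two sets were filmed after opposite sprays. Under balanced order, the consequence that does not depend on the order rule is lost precision: about 9-20% of the variance of each within-mother difference, if image-set variance is 10-25% of the other within-mother variance.

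Bias of (2p − 1)d arises only if two things are both true: Visit 3 order is systematically related to Visit 2 order, and the mother's spray alters the filmed images beyond matched affect. With orders always the same or always reversed, the bias is the full +d or −d and cannot be estimated from the data. The documents establish neither condition and give no value for d.

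A reader might infer that, because each mother's two scans use different images, the trial's oxytocin-placebo contrast is itself partly a contrast of two stimulus sets. That is true of one mother's difference. It is not supported for the group mean, because the pairing ties image set to period and the stated balance separates period from treatment. A reader might also infer that the two orders were in fact linked; the documents are silent on this.

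**What to change.** **If scanning has not been done.** Pool each mother's 2A and 2B images. Within each affect level, split them at random into two matched, non-overlapping sets, each with half its own-infant images from each session. Use one set at 3A and the other at 3B, and match the unknown faces to the same age mix. This needs no new visit or recording and the same number of unique images. The cost is small: frames from one filming session appear at both scans, so novelty at 3B is slightly lower, and each scan mixes two infant ages about a month apart.

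**If scanning is done.**
- State how Visit 3 order was assigned relative to Visit 2 order, and report order counts overall and by attachment group.
- Keep period (= image set) in the fMRI model whatever its p-value.
- Add spray at filming as a covariate where the orders allow separation. With balanced order, the cost is a variance factor for the treatment effect of 1/(1 − (2p − 1)²): 1.00 at p = 0.5 and 1/(1 − 0.25) = 1.33 at p = 0.75.
- If the orders were always the same or always reversed, state that the fMRI drug effect cannot be separated from an effect of the spray given when the images were recorded.

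These steps need only the allocation record and a re-run of the model.

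### The imaging ANOVA labels the spray both a within- and a between-subjects variable and names no error term for it, and the region-of-interest tests of the spray are not stated to be paired, although every mother is scanned under both sprays.

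*Combined protocol and SAP*

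**What the plan says.** The Study Protocol, under Visits 2A&B and 3A&B, describes a double-blind crossover: "Each participant was administered both the active (oxytocin) and inactive (placebo) nasal spray just prior to separate behavioral or fMRI scanning sessions". The sequence of the two sprays is balanced over mothers. Under Visit 3A&B, "each mother attended two scanning sessions at the Human Neuroimaging Laboratory", so there is one scan per spray.

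The SAP section on fMRI data processing and analysis models four face categories per scan (own or unknown infant, happy or sad). It then specifies a mixed-model repeated measures ANOVA with three fixed factors. Face category is a repeated within-subjects factor, attachment is a between-subjects factor, and treatment is entered "as a within- and between-subjects variable". On the random part it says: "Subjects were treated as a random effect within each group". The interaction it names for testing is face affect x treatment x attachment. No mother x spray (scan) term is mentioned, and no error term is assigned to any effect.

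The same paragraph compares mean betas in the a priori regions (VTA, ventral striatum, medial prefrontal cortex) between the two treatment groups and between the attachment groups. It uses a t-test and the Mann-Whitney U-test.

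The later section, Analyses by Hypotheses, tests Hypotheses 1-3 by a generalized estimating equation (GEE) model said to account for the crossover's repeated measures. That model starts with order and order x treatment terms. For brain outcomes it adds affect and the three-way interaction.

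**The concern.** No mother belongs to only one spray group. The between-mother factor that the crossover creates is order of administration, not treatment. A model cannot treat the spray as both within and between subjects without saying which comparison each label refers to, and the two readings need different error terms.

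The spray changes from scan to scan, and the four face betas from one scan share that day's state and scanner conditions. Spray and spray x attachment should therefore be tested against the variation of the spray difference between mothers (mother x spray).

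Two departures from this are open on the wording. If the spray is handled as between-subjects, a mother's two scans are treated as coming from different people, and the precision for which a crossover is chosen is lost. If only a mother intercept is fitted, the face betas within a scan count as independent replicates of the spray, and the spray test can become too liberal. The Mann-Whitney comparison of treatment groups shows that the first possibility is not fanciful, since that test ignores pairing.

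**Working it through.** **Inputs.** From the documents: 2 scans per mother, 4 face categories per scan, 4 attachment types. The documents give no sample size, alpha, power or variance, so there is no planned figure to reproduce. Everything below rests on assumed values, with a nominal two-sided 5% level.

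**1. Spray analysed as between-subjects.** Let rho be the correlation between a mother's two mean betas, each with variance s². The true variance of the mean difference over n mothers is 2s²(1-rho)/n. The unpaired analysis uses 2s²/n. The standard error is therefore too large by 1/sqrt(1-rho):

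- rho = 0.3: 1/sqrt(0.7) = 1.20
- rho = 0.5: 1/sqrt(0.5) = 1.41
- rho = 0.7: 1/sqrt(0.3) = 1.83

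For power, assume 30 mothers and set the effect so that the paired t-test has 80% power. In simulation the unpaired t-test on the same data has about 69%, 53% and 25% power. Its true type I error is about 2.0%, 0.7% and 0.1%.

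**2. Mother intercept only.** Take the residual variance of one beta as 1, mother x spray (scan-to-scan) variance as r, and mother x face variance as f. Within each mother there are 7 degrees of freedom, with these expected mean squares:

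- mother x spray (1 df): 1 + 4r
- mother x face (3 df): 1 + 2f
- mother x face x spray (3 df): 1

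The correct error for the spray is 1 + 4r. The intercept-only model pools all seven:

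[(1 + 4r) + 3(1 + 2f) + 3]/7 = 1 + (4r + 6f)/7.

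The variance ratio, true over modelled, is V = (1 + 4r)/[1 + (4r + 6f)/7]. The actual level is 2 x P(Z > 1.96/sqrt(V)). For example, with r = 0.5 and f = 0, V = 3/1.286 = 2.33 and the level is 19.9%.

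| r | f = 0 | f = 0.25 | f = 0.5 |
|---|---|---|---|
| 0.1 | 8.9% | 6.2% | 4.3% |
| 0.25 | 13.8% | 10.6% | 8.2% |
| 0.5 | 19.9% | 16.6% | 13.8% |
| 1.0 | 27.2% | 24.1% | 21.5% |

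Simulation (8,000 trials per setting, 20, 40 or 60 mothers in four equal attachment groups, mother variance 1, f = 0.25) agrees. The spray test runs at about 11%, 16-18% and 24-26% for r = 0.25, 0.5 and 1. The spray x attachment test runs at about 14-15%, 26-27% and 42%. More mothers do not cure it. With r = 0 and f = 0 both tests hold about 5%.

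The three-way test moves the other way. Its correct error is 1, but the pooled error is 1 + (4r + 6f)/7, which is larger. In the same simulations it rejects in about 0.8-1.0% of null trials at r = 0.25 and about 0.1% at r = 1.

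**3. Stratum-specific errors.** In all settings, testing spray and spray x attachment against mother x spray gives about 4.5-5.4%. Testing the three-way interaction against mother x face x spray gives 4.5-5.2%. A paired t-test on mean betas gives 4.6-5.4%.

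**The case against.** A reader might infer that the mother is the only random effect and that the oxytocin tests therefore have no valid error term. The documents do not support that. They name subjects as random but do not say that nothing else is. They also call the analysis a repeated measures ANOVA, whose conventional form tests each within-subject effect against its own subject-by-effect stratum, and step 3 shows that this holds the nominal level. The defect is an unspecified error term, not a proven absence of one. What remains is that the between-subjects label conflicts with the conventional form, so the text cannot be relied on to imply it.

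The label may also be loose wording. The protocol itself says that "maternal brain and behavioral responses to infant cues were assessed within and between subjects", which could mean order or a first-session comparison. Likewise, Mann-Whitney is a proper choice for attachment groups and may have been meant mainly for them. Both readings are possible, but the SAP states neither, and its sentence applies the tests to treatment groups as well.

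The GEE limits the reach of the problem. It carries the treatment, attachment and interaction terms for the brain outcomes and starts with order terms. A z-test with mother-clustered robust variance, used as a stand-in for it, ran at about 5-6% with 40-60 mothers and about 7% with 20. That objection stands, and it is wrong to read the point as covering every oxytocin test in the trial. It does not make the ANOVA harmless, because the SAP does not say which analysis governs the brain outcomes.

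**Conclusion.** The point holds for the imaging ANOVA and the region-of-interest comparisons, and only for those. The stated role of the spray contradicts the crossover, and its error term is not given.

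The direction of any error depends on how the model was fitted. Under a between-subjects analysis the spray test is too conservative, with the power loss in step 1 growing with the within-mother correlation. Under an intercept-only fit, spray and spray x attachment are too liberal when scan-to-scan variance is material, while the three-way interaction that the section names is too conservative. It would therefore be wrong to read the point as a general excess of false positives. Inflation of the spray test vanishes when scan-to-scan variance is zero. It can also vanish when that variance is small and mother x face variance is large (4.3% at r = 0.1, f = 0.5). Under stratum-specific errors there is no distortion.

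Every size given rests on assumed variances, correlations and numbers of mothers. The contradiction itself rests on none of them.

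**What to change.** In the SAP section on fMRI data processing and analysis:

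- Define the spray as a within-mother factor only, and delete the between-subjects label for it.
- State the error terms: mother x spray for spray and spray x attachment, mother x face for the face effects, and the mother x face x spray residual for the three-way test. A mother x spray term without mother x face would leave the same fault in the face tests.
- Use paired tests (paired t, Wilcoxon signed-rank) for the region-of-interest comparisons of the sprays. Unpaired tests may stay for attachment groups.
- Carry the order term from Analyses by Hypotheses into this ANOVA as its between-mother design factor.
- State whether the ANOVA or the GEE governs the brain outcomes.

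The cost is SAP wording and a re-run on existing data. The spray tests will have fewer error degrees of freedom than under a pooled residual (about one per mother instead of seven), so some p-values may become less favourable.
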